Medical Technician	11
Physician Assistant	10

Table 1: Observers divided by expertise category

Participants were asked why they chose to participate and given three choices, as shown in Table 2.

Compete With Others	37
Earn Money	248
Improve My Skills	518

Table 2: Observers divided by reason to participate

Participants reported coming from 78(!) countries with three quarters of the participants coming from nine countries, as shown in Table 3.

Philippines	198
USA	182
Ghana	94
Great Britain	31
Romania	30
Canada	27
Mexico	19
Indonesia	15
Australia	13
All other	194

Table 3: Reported country of origin.

Beyond this demographic information, we have only an observer number. We were given no identifying information about the participants. Participation on the app constituted consent. Procedures were approved by the Institutional Review Board at Brigham and Women's Hospital (IRB #2007P000646).

These 803 participants produced 311,842 trials of data. An excel spreadsheet with all data is posted on the Open Science Framework at <https://osf.io/hck5n/>. From this set, we eliminated participants who did not complete a full block of 80 trials. This left 630 participants who ran a total of 277,371 trials in 2,988 blocks. Different participants chose to participate in different numbers of blocks. As shown in Table 4.

Blocks Run	# of Participants		Blocks Run	# of Participants
1	315		13	10
2	178		14	2
3	104		15	4
4	56		16	6
5	52		17	5
6	22		18	3
7	27		19	10
8	20		20	3
9	14		21	4
10	10		22	2
11	10		23	6
12	5		24	4

Table 4: Numbers of participants who ran N (1-24) blocks over 6 days of testing.

Those participants running only a single block were removed from most analyses because our primary interest is the influence of one block upon the next. Obviously, with some participants contributing 24 blocks and others contributing 2, the dataset is unbalanced. We repeated the main analyses reported below, limiting the analysis to only the first pair of blocks for each observer. This reduces power. However, the main patterns of results, reported below, are found when the dataset is restricted to only blocks 1 and 2. Accordingly, we think that the unequal numbers of trials and blocks from different participants is not a significant issue for the present study. In the results reported, we analyze results from the 2,998 remaining blocks of data.

Statistical Analysis / Results

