To analyze the effect of one block on the next block, we derived all the pairs of blocks in the dataset. For each of the blocks, we calculated the true positive and false positive proportions and used these to derive the standard signal detection measure of d' and criterion (Note that we are refraining from using the term “sensitivity” because it is used to refer to d' in the behavioral science community and to the true positive rate in the medical community.) For the primary analyses, pairs were removed from analysis if either member of the pair produced a d' of less than 0.5. The task was relatively difficult and we had little control over the motivation of participants in online study of this sort. The probability of achieving a $d' > 0.5$ by guessing through an 80 trial block is $\sim 0.6\%$. A cutoff of 0.4 would permit over 2% of blocks to be pure guessing. A $d' > 0.5$ cutoff left 2,080 pairs of blocks. The distribution of those pairs is shown in

Table 5:

		Block N				
		Low, No Feedback	Low, Feedback	High, No Feedback	High, Feedback	
Block N+1	Low, No	29	140	151	134	454
	Low, Feed	92	110	150	218	570
	High, No	261	117	51	117	546
	High, Feed	147	218	118	27	510
		529	585	470	496	2080

Table 5: Counts of the 16 different pairs of Block N and Block N+1.

As can be seen, there is a good, if uneven distribution of pairs. There are fewer pairs on the diagonal where the condition is the same in Blocks N and N+1. In order to run the same block, twice in a row, participants needed to encounter that condition last on Day K and first on Day K+1 since the same condition could not be run twice on the same day. The marginals show that this distribution of the four different conditions is very roughly uniform.

First, we compare performance in the four conditions, regardless of their position the sequence of sessions for each observer. Figure 2 shows the signal detection measures of d' and criterion, “c”. These values cannot be computed if $p(\text{True Positive}) = 1.0$ or $p(\text{False Positive}) = 0.0$. Accordingly, in keeping with one standard practice, we add $\frac{1}{2}$ of a False Positive error to each False Positive count (Hautus, Macmillan, & Creelman, 2021).

[figure not shown]

Figure 2: D' and Criterion as a function of condition. Each dot represents one of 2080 blocks of data. Black lines show mean and +/- 95% CI of the mean.

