A one-way ANOVA shows a main effect of condition on d' ($F(3, 2076) = 6.461, p = 0.0002$, partial eta-sq = 0.01) and Šídák's multiple comparisons test shows that performance on skin cancer detection task is modestly better in the high prevalence, feedback condition than in the high prevalence, no-feedback condition ($p = 0.008$). Prevalence effects are better understood as criterion shifts. An ANOVA shows a very large main effect of condition on criterion ($F(3, 2076) = 30.16, p < 0.0001$, partial eta-sq = 0.04). Pairwise comparisons show a strong LPE effect when feedback is given ($p < 0.0001$). Criterion becomes more conservative at low prevalence. Without

feedback, criterion becomes slightly more liberal on average (0.34 to 0.31). This is not statistically significant ($p = 0.47$). As noted earlier, the PICC effect (Levari, et al., 2018), while certainly real, is typically more fragile than the LPE effect in the opposite direction (Lyu, et al., 2021). The differences between conditions with feedback and without feedback are highly significant ($p < 0.0001$ for each comparison). A significant LPE effect is seen if analysis is restricted to each participant's first block of data ($p < 0.0001$). There is no PICC effect. If all blocks of data are used, eliminating the $d' > 0.5$ filter, there is, again a significant LPE ($p < 0.0001$) and an insignificant PICC effect ($p = 0.1244$).

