each of these effects, we derive measures of d' and criterion for each of the 16 pairs (combinations of one of four 'first blocks' with one of four 'second blocks'). We then subtract a baseline derived from all blocks of the second block condition. We use the second blocks as the baseline because we are looking for a change in the second block. In fact, it doesn't make much difference. Many second blocks in one pair are the first blocks in a subsequent pair and the baselines would be very nearly the same if all blocks were included as in Figure 2 above. Thus, for example, to assess the influence on criterion of Low Prevalence without Feedback (Condition 1 in the figures to follow) on High Prevalence without Feedback (Cond 3), we compute $\text{Criterion}(\text{pair 13}) - \text{Criterion}(\text{Cond 3})$. This is done for each of the 2080 pairs of blocks using the $d' > 0.5$ filter. The data for each of these 2080 "good" pairs of blocks are posted on the Open Science Framework at <https://osf.io/hck5n/>.

Figure 4 shows the change in D' as a function of pair with each dot representing one pair of blocks. Statistical tests are simple T-tests against a null hypothesis of no change in d' from block 1 to block 2. Three pairs, forming no obvious pattern, reach statistical significance (all $p = \sim 0.02$, all Cohen's $d = \sim 0.2$). As these are not corrected for multiple comparisons, these should not be considered strong effects. The general picture is of little or no effect of the first block of trials on d' in the second block of trials.

[figure not shown]

Figure 4: Change in d' on block 2 as a function of the nature of block 1. X-axis gives numerical values for each member of a pair where 1 = low prevalence, no feedback, 2 = low prevalence, with feedback, 3 = high prevalence, no feedback, and 4 = high prevalence, with feedback. P-values show results for simple t-tests, testing against the null hypothesis that there is no change in d' . Black lines show means +/- 95% confidence intervals.

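### Figure 2 is described as covering all blocks but has N = 2,080, the number of filtered pairs; separately, its unadjusted condition means include the study's own carry-over, which probably understates the low-prevalence effect with feedback

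*Combined protocol and SAP*

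**What the plan says.** All references are to the Specific Protocol.

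- **Scope in words.** Statistical Analysis / Results introduces Figure 2 as a comparison of the four conditions "regardless of their position the sequence of sessions for each observer". The section on how one block influences the next says of its second-block baselines that "the baselines would be very nearly the same if all blocks were included as in Figure 2 above".
- **Scope in numbers.** The Figure 2 caption reads "Each dot represents one of 2080 blocks of data". Both one-way ANOVAs (on d' and on criterion) carry degrees of freedom 3 and 2076.
- **Where 2,080 comes from.** The d' filter "cutoff left 2,080 pairs of blocks". Table 5 breaks these down by the condition of the first and second block.
- **Blocks available before the filter.** Under Observers: "This left 630 participants who ran a total of 277,371 trials in 2,988 blocks". The end of the same section gives 2,998.
- **Carry-over.** The Figure 5 text reports that a low-prevalence block with feedback makes the next block more conservative and a high-prevalence block with feedback makes it more liberal, each with Cohen's d between 0.2 and 0.5. After a block without feedback it reports no effect, except perhaps before a high-prevalence feedback block (d = 0.18). The analysis of delay finds no fading with time.
- **Checks on the low-prevalence effect with feedback.** It is reported at p < 0.0001 in first blocks only, and at p < 0.0001 in all blocks without the d' filter. Neither check comes with an effect size.

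**The concern.** There are two separate problems.

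The first is labelling. A reader told that conditions are pooled over position, with all blocks included, cannot square that with an N equal to the number of pairs. The documents do not say which block of each pair was plotted and analysed, so the population behind the two ANOVAs is undefined.

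The second is bias in the condition means. If a block's criterion depends on the block before it, a condition's raw mean depends on what tended to precede it. The same type of contest could not be run twice in a day, so a high-prevalence feedback block rarely follows its own kind and often follows the low-prevalence feedback condition. The reverse also holds, less sharply. Each feedback condition is therefore pulled toward the other, and the contrast between them shrinks. At stake is the size of the low-prevalence effect with feedback and the meaning of the baselines subtracted for Figure 5.

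**Working it through.** **1. Reproduce the plan's N.** N = error df + groups = 2076 + 4 = 2,080. Table 5 row totals: 454 + 570 + 546 + 510 = 2,080. The reported effect sizes also follow from partial eta-squared = 3F / (3F + 2076): F = 6.461 gives 0.009 and F = 30.16 gives 0.042, matching the stated 0.01 and 0.04.

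**2. Can 2,080 be every block in those pairs?** No. Pairs overlap: the second block of one pair is often the first of the next. A run of k consecutive pairs holds k + 1 blocks, so 2,080 pairs contain 2,080 blocks plus one per run. One block per pair fits exactly. The expertise ANOVA shows the same pattern: error df 1863 + 4 = 1,867, and the Table 6 pairs sum to 131 + 952 + 426 + 358 = 1,867.

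**3. Predecessor mix of second blocks (Table 5 rows).** Let D be the carry-over in SD units: +D (conservative) after low prevalence with feedback, -D after high prevalence with feedback, 0 after no feedback.

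| Second block | After low, feedback | After high, feedback | Net shift of mean |
|---|---|---|---|
| Low, feedback | 110/570 | 218/570 | (110 - 218)/570 = -0.189 D |
| High, feedback | 218/510 | 27/510 | (218 - 27)/510 = +0.375 D |
| Low, no feedback | 140/454 | 134/454 | +0.013 D |
| High, no feedback | 117/546 | 117/546 | 0 |

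Understatement of the low-minus-high contrast with feedback: 0.375 + 0.189 = 0.564 D. The no-feedback contrast moves by only 0.013 D.

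**4. What D do the reported results allow?** The reported d values are deviations from second-block means, which already contain the shifts in step 3. With a common D and similar SDs:

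- Low feedback to high feedback: d = (1 - 0.375) D = 0.625 D. The lower limit of 0.2 gives D of at least 0.32.
- High feedback to high feedback: d = (1 + 0.375) D = 1.375 D. The upper limit of 0.5 gives D of at most 0.36. That pair's own result (n = 27, p = 0.017) implies d = 0.49, hence D = 0.36.
- Low feedback to low feedback (1.189 D) and high feedback to low feedback (0.811 D) allow D up to 0.42 and from 0.25, so they do not bind.

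D is therefore about 0.32 to 0.36, and the understatement is 0.564 × 0.32 = 0.18 to 0.564 × 0.364 = 0.21 SD. The limits of 0.2 and 0.5 are rounded in the documents, so these ends are approximate.

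**5. If second members were not used.** First members and an all-blocks set include some blocks with no predecessor.

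- All blocks: with 630 first blocks among 2,988, the share with a predecessor is 1 - 630/2,988 = 0.79, giving 0.79 × 0.564 = 0.445 D, or 0.14 to 0.16 SD.
- First members: the number of participants with two or more blocks is 630 - 315 = 315 from the stated total, or 557 from Table 4's own rows. The share is then 0.85 or 0.73, giving 0.48 D or 0.41 D, or 0.13 to 0.17 SD.

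Both lines assume the predecessor mix of step 3, which the documents do not give for these sets.

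**6. Figure 5 baselines.** These are second-block means, so they carry the shifts in step 3. A high-prevalence feedback block preceded by no feedback would appear shifted by -0.375 D, or 0.12 to 0.14 SD, with no carry-over at all. The reported d = 0.18 for such a pair is in that region if its sign is liberal; the sign is not stated. Taken literally, 0.18/0.375 gives D = 0.48, outside the range in step 4, so the simple model does not fit every figure.

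**The case against.** The strongest reply is that nothing here changes a conclusion. The bias runs toward the null, the low-prevalence effect with feedback is significant in spite of it, and the first-block check, which has no preceding block, agrees. The condition comparison is presented as a replication; the block-to-block effect is the main finding. A mean pooled over position is also a legitimate description. All of this stands, and it limits the point to labelling and effect size.

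Several stronger readings are tempting and are not supported:

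- **That N = 2,080 causes the bias.** It does not. An all-blocks set would carry the same effect, somewhat diluted.
- **That Figure 2 uses second blocks.** The documents do not say so. The sentence on baselines sets Figure 2 apart from the second-block set, which points the other way.
- **That 2,080 should have been 2,988.** That total precedes the d' filter and includes participants with a single block. The filter is disclosed. The right n for an all-blocks filtered set is not stated.
- **That the understatement runs from 0.11 to 0.28 SD.** This multiplies 0.564 by 0.2 and by 0.5 as if the reported d values were measured from a clean baseline. D = 0.5 would give d = 0.69 for the high-feedback repeat pair, above the reported maximum. D = 0.2 would give d = 0.13 for low feedback to high feedback, below the reported minimum.
- **That Figure 5 is overturned.** The same baseline is subtracted from every pair sharing a second-block condition, so differences between predecessors within that condition are unaffected. Only the tests against zero shift.

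**Conclusion.** The mismatch is certain: the words describe all blocks pooled over position, while the caption and df give the number of filtered pairs, consistent with one unspecified block per pair.

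The carry-over in the condition means follows from Table 5 and the study's own main finding. Its size is conditional. If second members were used, with a common symmetric shift, none after no-feedback blocks and similar SDs across cells, the low-prevalence effect with feedback is understated by about 0.18 to 0.21 SD. For first members or all blocks the bias is probably smaller, in the same direction. The no-feedback contrast is essentially unaffected (0.013 × 0.36, under 0.01 SD). The Figure 5 baselines carry the same shift.

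A reader might infer that the low-prevalence effect itself is in doubt. It is not: the first-block and unfiltered checks both give p < 0.0001. The feedback-condition means and SDs are not given in the text, so the size cannot be fixed more closely from the documents.

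**What to change.** 1. Define one analysis set for Figure 2 and its ANOVAs. Say whether it is the first member, the second member or every eligible block, and whether the d' filter applies. Make the n, the df, the caption, the sentence introducing Figure 2 and the later reference to all blocks agree with it. Reconcile the block totals at the same time: 2,988 and 2,998 both appear, and Table 4's rows sum to 872 participants and 3,409 blocks against the stated 630 participants.
2. Add the preceding block's condition to the condition model, with a level of none for first blocks, and report the condition contrasts at a common predecessor mix.
3. Report effect sizes and confidence intervals for the first-block analysis already run, as the check free of carry-over. It need not become primary.
4. State beside Figure 5 that its baselines are themselves means over an unequal mix of predecessors.

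The cost is one re-run model and corrected text, with no new data. The first-block estimates rest on at most one block per participant, so their intervals will be wider.

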The central question of the present study is how experience with one level of prevalence, with or without feedback, influences performance on subsequent trials where either prevalence and/or feedback conditions could have changed. In the great bulk of research on prevalence effects, high prevalence trials were followed by low prevalence trials or participants experienced only a single prevalence level. Typically, feedback is not independently manipulated (but see Grown & Kukucka, 2021; Lyu, et al., 2021; Papesh, Heisick, & Warner, 2018; Weatherford, Erickson, Thomas, Walker, & Schein, 2020). Moreover, in previous studies, the change due to a previous discrete block of trials was not assessed.

In the present study, prevalence can be high or low and feedback can be present or absent. This yields four conditions: Low prevalence with feedback, Low prevalence without feedback, High prevalence with feedback, and High prevalence without feedback. There are 16 possible pairings of two consecutive blocks. In this study, the stimuli are skin lesions: either nevi (skin 'moles'; singular, nevus) or melanoma (skin cancer). A large dataset of over 300,000 decisions was collected on-line by participants using a medical image labeling app ("DiagnosUs" <http://diagnosus.com/>). Participants had varying levels of expertise from complete novice to MD as will be described later. Thus, in addition to allowing us to assess the influence of one prevalence X feedback combination on another, these data provide new evidence about prevalence effects in expert populations (K K Evans, Birdwell, & [name], 2013; K. K. Evans, Tambouret, Wilbur, Evered, & [name], 2011; Evered, 2017; Mitroff, Ericson, & Sharpe, 2017;

Reed, Ryan, McEntee, Evanoff, & Brennan, 2011; Trueblood, et al., 2021; [name], Brunelli, Rubinstein, & Horowitz 2013).

To anticipate the broad outlines of the results, LPE and weak PICC effects are produced with these dermatology stimuli. As in other studies with expert populations, our experts show these effects, as do novices. In terms of the influence of one block of trials on the next block, we find that, in general, experience with a low prevalence block with feedback makes one more conservative in any subsequent block while the experience of high prevalence with feedback makes one more liberal. A block without feedback does not appear to have a significant impact on the next block.

Methods

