Data were collected on-line via a free and open iOS application, “DiagnosUs”, created by Centaur Labs as a platform for game-like image labeling competitions <https://www.centaurlabs.com/>). Between 6/22/21 and 6/27/21, Centaur Labs ran 24 ‘contests’ on our behalf, collecting >300,000 trials from 803 participants in 6 days. Each of the 24 contests consisted of 80 unique images of a skin lesion as shown in Figure 1. This is a relatively small number of images, but it kept the sessions short and encouraged participation. Images came from the International Skin Imaging Collaboration (ISIC) 2018 challenge (Codella, et al., 2019). The set contains over 1,200 melanoma images and over 7,600 nevus images.

[figure not shown]

Figure 1: Sample stimulus displays. Left: Participants are asked if a lesion is a melanoma (cancer) or a nevus (benign ‘mole’). Right: After response, if this were a feedback condition, red or green feedback would inform the observer of the correctness of the answer. In no feedback conditions, neutral feedback indicated that the response had been registered.

On each of the six days, there were four contests available. These were:

- 1) Low Prevalence – No Feedback; consisting of 20% (16) melanoma images
- 2) Low Prevalence – Feedback; prevalence was the same as in #1, but with accurate, trial by trial feedback
- 3) High Prevalence – No Feedback; consisting of 50% (40) melanoma images
- 4) High Prevalence – Feedback; prevalence was the same as in #3, but with accurate, trial by trial feedback

The contests were randomly assigned to participants with the constraint that they did not run the same type of contest more than once in a day. Participants could take part in as many or as few contests as they wished over the course of the six days and they could end up repeating a

condition from one day on another day. The prevalence and feedback conditions were not advertised to participants. Accuracy is the main dependent variable though we also collected response times.

Because of the on-line, voluntary nature of the data collection, we did not have control over the viewing conditions or the type of screen used. We compensated by collecting a very large dataset (see below).

Observers

We collected data from 803 unique individuals. For each individual, we have a crude categorization of expertise as shown in Table 1:

Medical Student	337
Pre-Med Student	174
No Medical Experience	145
Medical Doctor	54
Other Healthcare Professional	47
Nurse	25

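### The 2×2 prevalence-by-feedback comparison is tested by one-way ANOVAs on blocks treated as independent; the text omits the prevalence effect on d' and the criterion interaction, and calls a 4% effect very large

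*Combined protocol and SAP*

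**What the plan says.** The introduction to the Specific Protocol sets out two crossed factors: "In the present study, prevalence can be high or low and feedback can be present or absent". The Methods state that "Participants could take part in as many or as few contests as they wished over the course of the six days", and Table 4 shows between 1 and 24 blocks per person. For the analysis of successive blocks, "Those participants running only a single block were removed from most analyses".

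Under Statistical Analysis / Results the four conditions are compared first. The text counts 2,080 pairs of blocks; the Figure 2 caption says "Each dot represents one of 2080 blocks of data".

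- **d':** "A one-way ANOVA shows a main effect of condition on" d', with F(3, 2076) = 6.461, p = 0.0002 and partial eta-squared 0.01. The one follow-up in the text is feedback versus no feedback at high prevalence, p = 0.008 by Šídák's test.
- **Link to criterion:** the next sentence reads "Prevalence effects are better understood as criterion shifts".
- **Criterion:** "An ANOVA shows a very large main effect of condition on criterion", with F(3, 2076) = 30.16, p < 0.0001 and partial eta-squared 0.04. Low versus high prevalence has p < 0.0001 with feedback and p = 0.47 without (0.34 to 0.31, the opposite direction). Feedback versus no feedback has p < 0.0001 for each comparison.

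**The concern.** The test matches the design in neither structure nor error term. A factorial question is put to four unordered groups, and repeated blocks from one person enter as if they came from different people.

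Three statements depend on this. Reading prevalence as a matter of criterion needs the prevalence effect on d' to be shown, and the text does not show it. The LPE and prevalence-induced concept change (PICC) are presented as opposite effects separated by feedback, which is an interaction, yet no interaction is tested. And the wording about the size of the criterion effect does not fit the effect size printed beside it.

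**Working it through.** **Inputs.** The F values, df, p-values and 2,080 units come from Statistical Analysis / Results. Cell counts come from Table 5 and blocks per person from Table 4. The within-person correlation ρ and the number of pairs in the Šídák family, k, are not given, so ranges are used.

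**1. Reproduce the stated figures.** Partial eta-squared = 3F / (3F + 2076).
- d': 19.38 / (19.38 + 2076) = 0.0093, p = 0.00024 (stated 0.01 and 0.0002).
- Criterion: 90.48 / (90.48 + 2076) = 0.0418 (stated 0.04).

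Both agree.

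**2. Is there a participant term?** The error df are 2076 = 2080 − 4, so no. In Table 5 the same-condition pairs number 29 + 110 + 51 + 27 = 217. The other 2,080 − 217 = 1,863 pairs (89.6%) set two different conditions side by side in one person.

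**3. Split of the d' effect.** The between-condition sum of squares is 3 × 6.461 = 19.38 in units of the mean squared error. The reported contrast takes t² of it, and the remainder has 2 df (high prevalence pooled, low without feedback, low with feedback).
- Šídák over k = 6: single-test p = 1 − (1 − 0.008)^(1/6) = 0.00134, t = 3.212, t² = 10.32. The remainder is 9.07, so F(2, 2076) = 4.53, p = 0.011.
- p = 0.008 taken as unadjusted (k = 1): t = 2.655, t² = 7.05. The remainder is 12.33, so F = 6.17, p = 0.002.

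The contrast in the text thus carries 53% (k = 6) or 36% (k = 1) of the d' effect, and the rest is not described there.

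**4. How far the missing participant term could matter.** If condition varied wholly within person, F would become about F / (1 − ρ). If wholly between persons, it would become about F / (1 + (n − 1)ρ), with n pairs per person. Assume ρ = 0.2 to 0.5. Table 4 sums to 872 people although the text says 630, so n is 2080 / (872 − 315) = 3.73 or 2080 / (630 − 315) = 6.60.

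| Test | As run | Wholly within | Wholly between |
|---|---|---|---|
| d', 3 df | 6.46 | 8.1 to 12.9 | 4.2 to 1.7 |
| d' remainder, 2 df (k = 6) | 4.53 | 5.7 to 9.1 | 2.9 to 1.2 |
| Criterion, 3 df | 30.16 | 37.7 to 60.3 | 19.5 to 7.9 |

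At the between-person bounds the d' remainder has p of about 0.05 to 0.30 (300 error df assumed). Criterion stays clearly significant throughout.

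**5. Criterion interaction.** The two prevalence effects have opposite signs. With similar standard errors and the plan's own error term, the interaction t is at least (t without feedback + t with feedback) / √2.
- k = 6: (1.644 + 4.316) / 1.414 = 4.2.
- k = 1: (0.723 + 3.898) / 1.414 = 3.3.

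**6. The size label.** Condition accounts for 4.2% of the variance in criterion and leaves 95.8%. Under Effects of Expertise, the same document describes a partial eta-squared of 0.01 on criterion as very modest.

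**The case against.** Several objections stand.

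- **Capability.** A four-cell one-way ANOVA fits the same four means as a 2×2 model, and its pairwise comparisons can give the prevalence effect on d'. The gap is in what the text reports. Figure 2 is not shown in the text available here and may mark more pairs.
- **What the d' remainder proves.** A reader might infer that d' must also differ by prevalence. The documents do not support that. The remainder test borrows the independent-blocks error term that is itself in question, and it does not say which factor is responsible.
- **How strong the plan's claim is.** The introduction to the Specific Protocol calls the effect largely, not wholly, a criterion shift, and the Results report a significant d' effect.
- **Criterion conclusions.** All four simple effects are given. The LPE is also reported in each participant's first block alone (p < 0.0001), where blocks are independent. A formal interaction test would probably confirm what the simple effects suggest.
- **Clustering.** The plan acknowledges imbalance and says that the main patterns persist in the first pair of blocks per person. That check supplies neither factorial effects nor a participant-level error term.
- **Role.** This comparison precedes the key question, the effect of one block on the next, whose t-tests do not use these ANOVAs.

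One objection carries less weight: that printing 0.04 in the same sentence makes the label harmless. The label describes the effect, and the figure contradicts it.

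**Conclusion.** The point holds as a fault of analysis and reporting. The independent-blocks error term is wrong for these data, and the documents do not fix the direction of the error. They therefore do not support saying that the standard errors are simply too large, or promising a gain in precision.

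For d', 47% of the between-condition effect (k = 6; 64% if k = 1) is left undescribed in the text. That part is significant under the plan's own error term, but not securely once clustering is allowed for. For criterion, the missing item is the interaction test, and very large is not a fair description of 0.04.

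Two further inferences are tempting and unsupported. Undoing a six-pair Šídák adjustment would turn the unfiltered PICC p = 0.1244 into 1 − (1 − 0.1244)^(1/6) = 0.022, but the text does not say that this p-value was adjusted. Relabelling the criterion effect as small would rest on the same faulty error term: removing person variance at an assumed correlation of 0.3 to 0.5 would raise partial eta-squared to 0.0418 / (0.0418 + 0.9582 × 0.7) = 0.059, or to 0.080 with 0.5 in place of 0.7.

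**What to change.** Re-analyse the posted data with a prevalence × feedback model that includes a participant random intercept. For both d' and criterion, report the two main effects and the interaction, each with an estimate and 95% CI. Give the prevalence effect on d' before the sentence that reads prevalence effects as criterion shifts. Say which block of each pair enters the model, since text and caption differ on whether the 2,080 units are pairs or blocks. State whether the LPE and PICC contrasts are adjusted for multiplicity, and over how many comparisons. Delete very large and let the reported effect size stand.

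The model will inherit the exclusion of pairs with d' below 0.5 and the half-count added to false positives, so the d' estimates should be read with both in mind.

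The cost is a short re-analysis, a few sentences and a less favourable description of the criterion effect. No new data are needed.
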